[figure not shown]
Pre-registration for quantitative part of Art on Prescription

[figure not shown]

Athens March, 10, 2024

Design

Stratified randomised controlled trial with two arms: arts intervention (any of the arts interventions, see list), which the investigators call here Active Group (AG) vs waitlist control (WL). Stratifying will happen at each site.

REMEMBER the investigators want to measure AG and WL, then WL becomes AG after 3 months and both the initial AG and the WL \rightarrow AG will be measured in exactly the same way for another 3 months.

AG for 3 months. Then goes into 3 month follow up.

WL for 3 months. Then this group receives intervention and becomes AG and has measurements for 3 months as the AG did.

There will be a 2-month break between T3 and T4 due to summer vacation

In the beginning, an open invitation to institutions of culture and mental health had been sent. Culture institutions i.e. Opera House, Contemporary Art Museum, National Theater etc. presented their action plans for interventional courses. Investigators did the connection between mental health and culture institutions.

Potential participants declared their preference for the interventional course such as dance, cinema etc. and they listed while an external investigator did the blind randomization into AG or WL group.

Measurement

Participants in both the AG and the WL groups will be measured on the following outcomes. Primary Outcome: Wellbeing Questionnaire (WEMWBS), PHQ-9, GAD-7 Secondary Outcomes: UCLA-20.

Frequency of Measurement:

→ The primary outcome will be measured at time points (for adults):

- T0: (before the randomisation; patient's personal data and demographics)
- T1: (before the start of the intervention for the active group or the entry into the study for the WL group)
- T2: 6 weeks (after the start of the intervention for the active group or the entry into the study for the WL group)
- T3: 12 weeks (after the start of the intervention for the active group or the entry into the study for the WL group)

The secondary outcomes will be measured at time points 0 (T4) and 12 weeks (T5) for both AG and WL.

→The primary outcome will be measured at time points (for children/adolescents):

- T0: (before the randomisation; patient's personal data and demographics)
- T1: (before the start of the intervention for the active group or the entry into the study for the WL group)
- T3: 12 weeks (after the start of the intervention for the active group or the entry into the study for the WL group)

The secondary outcomes will be measured at time points 0 (T4) and 12 weeks (T5) for both AG and WL.

Model

The investigators will follow standard practice for RCTs and apply an ANCOVA model to estimate the effects of treatment. The formalism is:

y ~ b0 + b1xtreatment_group + b2xtime + b3xtreatment_groupxtime + covariates (1)

Where, y is each outcome, b1-b3 are the regression coefficients and covariates denote covariates at randomisation (DETERMINE)

The inference of interest for the model concerns b3, the interaction term, as the investigators posit that there will be a difference in slopes between the treatment groups.

The inference is going to happen via an estimation of the t-statistic, defined as follows"

t = b3/SE(2)

Where SE is the standard error for coefficient b3

[figure not shown]
t > 1.96(3)

And 1.96 is the critical value for statistical significance at alpha = 0.05.

Target Sample Size per Arm

Parameters:

- power = 0.8
- alpha = 0.05
- Correlation between time points = 0.6 (a conservative estimate based on https://www.ncbi.nlm.nih.gov/pmc/articles/PMC2222612/)
- Effect size corresponding to d = 0.5

library(tidyverse) # for data wrangling library(faux) # for simulation

library(broom) # for tidy analysis results

set.seed(1974)

I will simulate the following

```

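### Randomisation is stratified by site, but equation (1) lets only treatment act on change over time, so site differences in change stay in the error of b3; it is also unstated whether adults and children are pooled

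*Protocol*

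**What the plan says.** - **Randomisation (Design).** There are two arms, arts intervention and waitlist, and "Stratifying will happen at each site". No other stratification factor is named.
- **Schedules (Measurement, Frequency of Measurement).** There are two lists. The one headed "The primary outcome will be measured at time points (for adults" gives baseline T1, a six-week visit ("T2: 6 weeks (after the start of the intervention for the active group or the entry into the study for the WL group") and T3 at 12 weeks. The one headed "The primary outcome will be measured at time points (for children/adolescents" gives T1 and T3 with no T2.
- **Model.** The analysis is called ANCOVA and is written as "y ~ b0 + b1xtreatment_group + b2xtime + b3xtreatment_groupxtime + covariates (1". One equation serves all outcomes: "Where, y is each outcome, b1-b3 are the regression coefficients". The adjustment set is open: "covariates denote covariates at randomisation (DETERMINE". The test is on one coefficient: "The inference of interest for the model concerns b3, the interaction term".
- **Simulation code (Target Sample Size per Arm).** The fitted model has time, group and their interaction. It has no site, age group or subject term, and every simulated person has four measurements.
- **Pooling.** Nothing says whether adults and children/adolescents enter one fit or two.

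**The concern.** Stratifying by site balances site between the arms. The precision that this buys reaches the analysis only if site differences are taken out of the residual of the tested contrast. Here that contrast is a difference in change. A covariate that is constant over time and enters as a main effect shifts a person's T1 and T3 scores equally, so it cancels from that person's change. Writing site into the open slot would therefore look like adjustment for the stratification factor without being one for b3. At stake is some precision and a test that runs below its nominal level.

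The second matter is what b3 means. The protocol sets up two populations with separate schedules and gives one equation, one b3 and one sample size per arm. If both are fitted together, b3 is an average over adults and children whose weights are set by recruitment. A reader could not tell which population carries it.

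**Working it through.** The protocol prints no sample size or achieved power, so there is no stated figure to reproduce. Re-running its code (SD 10.4, d = 0.5, four time points) first passes 80% power at about 160 per arm.

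**1. Standard error with and without site on change**

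From the protocol: correlation r = 0.6 (parameter list) or 0.5 (live code), two-sided critical value 1.96, d = 0.5. Assumed: outcome SD 1, S = 10 sites of 20, 1:1 within site (n = 100 per arm), one T1-to-T3 change per person, and between-site SD of mean change τ from 0 to 0.5.

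- Variance of change within site: 2(1 − r), which is 0.8 at r = 0.6.
- True SE of the arm difference, site being balanced: √[2(1 − r) × 2/n] = √(0.8 × 0.02) = 0.126.
- Model SE without site on change: √{[2(1 − r) + τ²(S − 1)/S] × 2/n}.
- Size of the test: 2Φ(−1.96 × ratio of model SE to true SE).

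| τ | Model SE, r = 0.6 | Ratio to 0.126 | Size |
|---|---|---|---|
| 0 | 0.126 | 1.00 | 0.050 |
| 0.1 | 0.127 | 1.01 | 0.049 |
| 0.2 | 0.129 | 1.02 | 0.045 |
| 0.3 | 0.133 | 1.05 | 0.040 |
| 0.5 | 0.143 | 1.13 | 0.027 |

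Simulation of 4,000 trials per setting gives the same SEs, with size from 0.052 at τ = 0 to 0.029 at τ = 0.5. With site on change, the SE stays at 0.126 throughout. At r = 0.5 the SE runs from 0.141 to 0.156, a ratio of at most 1.11. The top of the range is large: 0.5 × 10.4 = 5.2 points between sites, as big as the assumed treatment effect.

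**2. The two remedies compared**

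T3 on T1, arm and site has residual variance 1 − r², against 2(1 − r) for change.

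- r = 0.6: √(0.64/0.80) = 0.894, an SE about 11% smaller.
- r = 0.5: √(0.75/1.00) = 0.866, about 13% smaller.

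With 15 sites of 20 and r = 0.6, the SE is 0.8 × √(2/150) = 0.092. Change without site gives 0.103 (τ = 0) to 0.117 (τ = 0.5).

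**3. Effect on power at the protocol's d**

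Take d = 0.5 as reached at 12 weeks. Power is Φ(0.5/true SE − 1.96 × ratio).

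- 150 per arm, 15 sites, τ from 0 to 0.5: 99.8% to 99.6% at r = 0.6, and 99.1% to 98.4% at r = 0.5.
- 100 per arm, 10 sites: 97.7% to 95.9%, and 94.2% to 91.4%.

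**4. What b3 is if adults and children are pooled**

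Adult times 0, 6, 12 have mean 6 and sum of squares 36 + 0 + 36 = 72. Child times 0, 12 have mean 6 and sum of squares 36 + 36 = 72. Each person therefore carries equal weight in a linear slope, and b3 × 12 is the head-count-weighted mean of the two effects. For illustration, with 0.5 in adults and 0 in children:

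- 50% adults: 0.5 × 0.5 = 0.25
- 70% adults: 0.7 × 0.5 = 0.35
- 90% adults: 0.9 × 0.5 = 0.45

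Solving equation (1) by least squares gives the same values.

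**5. Equation (1) read literally, with no subject term**

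The residual variance is then 1 instead of 1 − r, so the SE of b3 is 1/√(1 − r) times the true one: 1.58 at r = 0.6 and 1.41 at r = 0.5. The size is 2Φ(−3.10) = 0.002 or 2Φ(−2.77) = 0.006. Steps 1 to 3 therefore apply once the analysis is at person level.

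**The case against.** **The covariate slot is open and may be settled in a statistical analysis plan.** This stands as far as naming covariates goes: leaving site unnamed is no fault. The slot is additive, however, and the form of the model and the tested coefficient are already fixed. A main effect of site cannot do the job for b3.

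**The size rests on assumptions.** This stands. The number of sites and the variance between them are not in the protocol, and the loss is nil if sites do not differ. Any error is conservative.

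**Without a subject term the problem is a different one.** This also stands. Step 5 shows a far larger distortion from that omission, and adding site by time alone would not bring the size to 5%. In that literal model a site main effect would also lower the residual variance. The site point concerns what remains once the analysis is at person level.

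Four stronger readings are tempting but not supported:

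- *The standard error is too small, as when clustering is ignored.* Randomisation is within site, so the error runs the other way. It would be too small only if the treatment effect itself varied across sites treated as random (assumed SD 0.2 to 0.3: size about 0.07 to 0.11). The protocol gives no ground for assuming that.
- *Power is badly damaged.* At the protocol's d = 0.5 and 150 per arm, the loss from site is under one point; at 100 per arm it is two to three. A large fall appears only if a smaller effect is chosen so that the trial sits at 80% to begin with.
- *Adults and children are pooled.* One equation and one sample size suggest it, but the text does not say so, and it describes a separate scale for children and adolescents (SDQ).
- *The missing T2 in children distorts b3.* Under linear time it does not (step 4). With time as a factor, T2 rests on adults in both arms, so the shift in composition falls mainly on the time term.

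**Conclusion.** The point holds as a worthwhile, low-cost improvement and not as a threat to validity. The analysis does not use the randomisation stratum where it matters, on change. In a person-level analysis this makes the standard error about 0 to 13% too large over assumed site SDs of 0 to 0.5. The test is conservative, with size down to about 0.03 at the extreme, and nothing is lost if sites do not differ. The bigger gain comes from the T1-adjusted form, whose SE is 11 to 13% smaller than that of change whatever the site variance.

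The age-group part is conditional. The protocol should say whether the two populations are pooled. If they are, b3 is a head-count-weighted mean. That is a legitimate average, but it needs labelling and should not be read as evidence for either group alone.

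**What to change.** 1. Analyse by the randomisation stratum. Preferably model T3 on T1, arm and site, which also matches the ANCOVA label in the Model section. Alternatively, use a repeated-measures model with a subject term and add site by time. These are alternatives, not equivalents; name one as primary.
2. State whether adults and children/adolescents are analysed together or separately.
3. If together, add age group on change (age group by time, or age group as a covariate in the T3 model), using the age collected at T0. This sharpens the estimate but leaves b3 an average, so also report the treatment effect separately by age group beside the pooled value.
4. Label any T2 estimate as adults only.

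The cost is one line in the model and one extra results table. A few degrees of freedom are used, with no measurable loss if sites do not differ. No new data or participants are needed.

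### The Design promises identical measurement of both arms for a further 3 months, but the schedule collects the primary outcomes only to T3, and model (1) does not say which visits it uses

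*Protocol*

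**What the plan says.** The Design section describes two phases. AG has the intervention first: "AG for 3 months. Then goes into 3 month follow up". WL waits and then crosses over: "WL for 3 months. Then this group receives intervention and becomes AG and has measurements for 3 months as the AG did". Of the original AG and the converted WL together it says: "AG will be measured in exactly the same way for another 3 months". Between the phases, "There will be a 2-month break between T3 and T4 due to summer vacation".

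The primary outcomes are WEMWBS, PHQ-9 and GAD-7; the secondary outcome is UCLA-20. Under Frequency of Measurement, the list headed "The primary outcome will be measured at time points (for adults") has T0 (personal data and demographics), T1, T2 at 6 weeks and, as its last entry, "T3: 12 weeks (after the start of the intervention for the active group or the entry into the study for the WL group"). The list for children and adolescents omits T2 and also ends at T3. After each list comes the only statement about later visits: "The secondary outcomes will be measured at time points 0 (T4) and 12 weeks (T5) for both AG and WL".

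The Model section gives one equation for every outcome, "y ~ b0 + b1xtreatment_group + b2xtime + b3xtreatment_groupxtime + covariates (1"), and places the inference on b3, tested by a single t-statistic as a difference in slopes. It does not say which visits enter, and it has no term for phase or crossover.

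**The concern.** The Design and the schedule cannot both be followed. The schedule determines what sites collect, so if it governs, the second phase produces no WEMWBS, PHQ-9 or GAD-7 score in either arm. The two questions that phase could answer on these outcomes, whether AG's gain lasts and whether WL improves once it gets the intervention, then go unanswered. An analysis plan written later cannot recover questionnaires that were never given.

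If the Design governs instead, the scores will exist, and a second question opens. Model (1) keeps a fixed group label and has no visit limit, yet from T4 onwards WL is the arm receiving the intervention. Putting those scores into the same b3 would mix the randomised contrast with its reverse.

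**Working it through.** **1. The texts side by side (primary outcomes)**

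| | T1 | T2 (6 wk) | T3 (12 wk) | T4 | 6 wk into phase 2 | T5 |
|---|---|---|---|---|---|---|
| Design, taken literally, adults | yes | yes | yes | yes | yes | yes |
| Schedule, adults | yes | yes | yes | no | no | no |
| Schedule, children/adolescents | yes | no | yes | no | no | no |

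The simulation under Target Sample Size per Arm differs again. It has four measurements labelled T1 to T4, with control means flat throughout. That matches neither three primary visits nor a waitlist that crosses over. The labels may simply be renumbered; the text does not say.

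**2. Timing of AG follow-up.** AG finishes at T3. With the 2-month break, T4 is about 2 months after that. T5 is 12 weeks later, so about 5 months after.

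**3. What pooling would do to b3.** The protocol states no figure for this, so there is none to reproduce. With complete, balanced data, b3 is the least-squares slope on time of the AG minus WL mean difference D.

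Inputs: visit weeks from the schedule; a break of 9 weeks (8 as a check); d = 0.5 from the sample-size parameters. Assumptions: the gain builds linearly over each arm's own 12-week intervention, WL is flat until T4, WL then gains the same 0.5 SD by T5, and AG keeps a fraction k of its gain at T4 and T5.

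- T1–T3 only: t = 0, 6, 12 and D = 0, 0.25, 0.5. Slope = 0.5/12 per week, or **0.50 SD per 12 weeks**.
- T1–T5: t = 0, 6, 12, 21, 33, mean 14.4, Sxx = 673.2. Slope = (ΣDt − ΣD × 14.4)/673.2.

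| AG keeps | D at T1 to T5 | ΣDt | ΣD × 14.4 | Slope × 12 |
|---|---|---|---|---|
| all (k = 1) | 0, 0.25, 0.5, 0.5, 0 | 18.0 | 18.0 | **0.000** |
| half (k = 0.5) | 0, 0.25, 0.5, 0.25, -0.25 | 4.5 | 10.8 | **-0.112** |
| none (k = 0) | 0, 0.25, 0.5, 0, -0.5 | -9.0 | 3.6 | **-0.225** |

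An 8-week break gives 0.000, -0.115 and -0.231. For k = 1 the zero holds for any break of b weeks: ΣDt = 13.5 + 0.5b, and ΣD × mean t = 1.25 × (10.8 + 0.4b) = 13.5 + 0.5b.

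**4. Dependence on how time is coded.** With visit numbers 1 to 5 (Sxx = 10), the slope for k = 1 is (−0.25 + 0.5)/10 = 0.025 SD per step. The T1–T3 value is 0.25, so 10% remains. For k = 0.5 it is -0.05 per step, and for k = 0 it is -0.125. With time as a factor, as in the protocol's own code, the omnibus interaction does not cancel: on the pooled k = 1 pattern, simulation gave about 83% power at an illustrative 100 per arm and r = 0.6.

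**The case against.** The strongest reply is that nothing in the protocol says T4 or T5 primary scores go into b3. The only explicit primary schedule stops before crossover, and the simulation holds the control arm flat, which suits an uncrossed comparison. On that reading b3 is a T1–T3 contrast and is intact, and which visits enter each model is often left to the analysis plan. This stands. A reader might infer that the primary test is cancelled by design; the documents do not support that. Cancellation needs pooling, linear time, a sustained AG gain and an equal WL gain, and it is exact only in calendar time. A single b3 with a t-test does imply linear time, but the code uses factor time.

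A reader might also infer that the 3-month follow-up is not measured at all. That goes too far. T4 to T5 is a 12-week window in which UCLA-20 is scheduled, and on the Design reading the primary outcomes would be measured there too. What remains is that the window opens about 2 months after AG finishes, and the wording should say so.

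Nor can one put a power figure on the lost WL before–after comparison. The protocol gives no sample size, only a simulation grid of 20 to 300 per arm, and it does not make that comparison a test.

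The reply does not remove the conflict over what is collected. That is a matter for the protocol, and a later analysis plan cannot repair it.

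**Conclusion.** The contradiction is on the face of the protocol and should be resolved. Under the schedule as written, AG durability and the response of WL under intervention have no data on any of the three primary outcomes, although the Design says both arms are measured alike in that period. The randomised T1–T3 comparison is not damaged by this.

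The effect on b3 is a conditional risk, not the stated analysis. If post-crossover scores were pooled in model (1) under the assumptions above, b3 would fall from 0.50 SD per 12 weeks to about 0, -0.11 or -0.23 as AG keeps all, half or none of its gain. By visit number, about 10% of the T1–T3 slope would remain in the first case. The 0.5 SD effect is the protocol's planning value; the retention fractions and the equal WL gain are assumptions made here.

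**What to change.** - Reconcile the Design with the schedule by adding WEMWBS, PHQ-9 and GAD-7 at T4 and T5 for both arms.
- For adults, either add the 6-week measurement in the second phase or drop the claim that measurement is identical. T4 and T5 alone do not reproduce the 0, 6 and 12-week pattern of the first phase.
- State in the Model section that the confirmatory b3 uses T1–T3 only.
- Analyse T4–T5 separately and label it non-confirmatory: AG maintenance from T3, and WL change from T4 to T5, or a model with a time-varying intervention indicator.
- Describe AG follow-up as about 2 and about 5 months after its intervention ends.
- Align the visit labels and number of measurements in the simulation with the schedule.

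The cost is 30 short items (14 + 9 + 7) at each of two visits already planned for UCLA-20, plus a few sentences. Keeping the identical-measurement wording for adults would also require a 6-week contact in the second phase.

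### The stated 3-month waiting and follow-up periods do not fit the 2-month summer break, and T4, the last visit with an untreated randomised comparator on that calendar, has no primary outcome listed

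*Protocol*

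**What the plan says.** **Durations (Protocol, Design).** For the active group: "AG for 3 months. Then goes into 3 month follow up". For the waitlist: "WL for 3 months. Then this group receives intervention and becomes AG and has measurements for 3 months as the AG did". The same section adds "There will be a 2-month break between T3 and T4 due to summer vacation".

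**Second phase (Design).** "both the initial AG and the WL \rightarrow AG will be measured in exactly the same way for another 3 months".

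**Visits (Measurement, Frequency of Measurement).** The list for the primary outcome ends with "T3: 12 weeks (after the start of the intervention for the active group or the entry into the study for the WL group"). Adults have T0 to T3; children and adolescents have T0, T1 and T3. T0 is described as personal data and demographics. For the later visits: "The secondary outcomes will be measured at time points 0 (T4) and 12 weeks (T5) for both AG and WL". The primary outcomes are WEMWBS, PHQ-9 and GAD-7, and the only secondary outcome named is the UCLA scale.

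**Analysis (Model).** "The inference of interest for the model concerns b3, the interaction term". The model is meant for each outcome, and its time points are not named.

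**Sample size (Target Sample Size per Arm).** The simulation has four measurements, T1 to T4, in both groups. WL is flat throughout, and AG moves in equal steps to the full d = 0.5 at T4.

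**The concern.** The durations and the break cannot all hold on one calendar. Under the visit schedule, AG has no assessment 3 months after its course, and WL waits longer than 3 months.

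The timing also decides which comparisons are randomised. If WL starts its course at T4, a T4 assessment taken beforehand still compares AG with an untreated randomised group, about 2 months after AG finished. By T5 WL has had the course. If the primary scales are not given at T4, that comparison is lost for them, and no later analysis plan can recover data that were not collected.

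UCLA has the reverse problem. T4 and T5 are its only listed times, so a group-by-time term fitted to those data would set AG in follow-up against WL under treatment.

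**Working it through.** **1. Calendar.** Inputs: T1 = week 0; T3 = week 12 (Frequency of Measurement); break of 2 months (Design); T5 = T4 + 12 weeks (Frequency of Measurement). One month = 365.25/12/7 = 4.35 weeks. I take AG's course to end at T3 and try 2 months as 8, 8.7 and 9 weeks.

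| Break (weeks) | T4 = 12 + break | T5 = T4 + 12 | AG, course end to T4 | AG, course end to T5 | WL wait, T1 to T4 |
|---|---|---|---|---|---|
| 8 | week 20 | week 32 | 1.84 months | 4.60 months | 4.60 months |
| 8.7 | week 20.7 | week 32.7 | 2.00 months | 4.76 months | 4.76 months |
| 9 | week 21 | week 33 | 2.07 months | 4.83 months | 4.83 months |

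The stated 3-month wait is not reproduced: 20.7/12 = 1.72 times the 12 weeks to T3. The last column assumes that the WL course starts at T4. The protocol implies this by labelling T4 as time 0 of the second phase but does not say it outright.

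**2. What each contrast estimates.** As an illustration, suppose AG keeps all of d = 0.5 and WL gains d = 0.5 from its own course.

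- AG minus WL at T4: 0.5 - 0 = 0.5.
- AG minus WL at T5: 0.5 - 0.5 = 0, although nothing has been lost.
- Group-by-time term over T4 to T5: AG change 0 minus WL change 0.5 = -0.5, which favours WL although the course works equally in both arms.

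**3. Schedule against simulation.** The simulated effect is 0.5 x 10.4 = 5.2 points at T4, and two thirds of it, d = 0.33, at T3. I re-ran the simulation with the group-by-time test as coded (1,500 runs per sample size).

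| Measurements | r | Power at 160 per arm | Power at 300 per arm |
|---|---|---|---|
| T1 to T4 | 0.5 | 85% | 99% |
| T1 to T4 | 0.6 | 86% | above 99% |
| T1 to T3, same path | 0.5 | 36% | 78% |
| T1 to T3, same path | 0.6 | 34% | 80% |

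With T1 to T4, 160 per arm is the first point on the protocol's grid above 80%. The drop depends on where the effect is reached. The test responds to the spread of the group differences over time, in SD units:

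- T1 to T4 (0, 0.167, 0.333, 0.5): sum of squared deviations 0.139.
- T1 to T3 on the same path (0, 0.167, 0.333): 0.056.
- T1 to T3 with the full d at T3 (0, 0.25, 0.5): 0.125.

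So the large loss follows from the simulation's own path cut at T3. It would be much smaller if d = 0.5 were meant to be reached at T3.

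**4. Would a T4 contrast be informative?** The protocol states no number per arm, so 80 and 160 are assumptions. The simulation gives r = 0.5 in code and 0.6 in text. With adjustment for the T1 score, SE = sqrt(2(1 - r²)/n) in SD units:

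- n = 80: r = 0.5 gives sqrt(1.5/80) = 0.137, 95% interval ±0.27; r = 0.6 gives sqrt(1.28/80) = 0.126, ±0.25.
- n = 160: r = 0.5 gives sqrt(1.5/160) = 0.097, ±0.19; r = 0.6 gives sqrt(1.28/160) = 0.089, ±0.18.

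Dropout and clustering by course are ignored. Against a target of 0.5, each of these half-widths is useful.

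**The case against.** **T4 is in the plan.** A reader might infer that T4 serves only as the starting value of a second phase. The documents do not support that: the simulation uses T4 as its final randomised measurement, with WL untreated and the whole effect present.

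**A controlled follow-up estimate is not excluded.** A reader might also infer that persistence of benefit has no controlled estimate at all. That goes too far. Both arms are measured at T4, at least on UCLA; the model does not name its time points; and the Design's promise of identical measurement can be read as including the primary scales.

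**The follow-up label may be innocent.** T4 to T5 is 12 weeks, so a phase of about 3 months exists, and the break is disclosed in the same section. The protocol does not say that T5 would be reported as 3 months after the course, and it states no durability hypothesis.

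**The simulation's T4 may be only a label.** The primary-outcome list for adults has four entries, T0 to T3. If the scales were also given at T0, the simulation could be those four visits renumbered. But T0 and T1 both precede the course, whereas the simulation moves AG by a third of the effect between its first and second points. A mismatch remains either way.

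**Analysis detail and crossover.** The choice of follow-up contrast is often left to the analysis plan, and loss of the untreated comparator after crossover is inherent in a waitlist design. Both are fair, and I do not count them as errors. What stands is narrower: the durations conflict, and the visit schedule, which is fixed in this document, lists no primary scale at T4.

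**Conclusion.** The concern holds in a limited form. The 3-month statements and the 2-month break are inconsistent. On the visit schedule AG is seen about 2 and 4.8 months after its course and WL waits about 4.8 months, against 3 stated. The calendar assumes that AG's course ends at T3; the WL figure also assumes that the WL course starts at T4. If WL instead crosses over at T3, as "WL becomes AG after 3 months" could be read, T4 is no longer an untreated comparison, which is a further reason to settle the point.

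The T4 outcome list conflicts with two other parts of the protocol. No AG-WL contrast at T4 is specified, and none against an untreated group is possible at T5. The T5 and T4-to-T5 figures above illustrate the effect of crossover under full retention and equal gain; they do not predict results. The 80 and 160 per arm are assumptions only. This is an inexpensive improvement and does not undermine the T1-to-T3 comparison.

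**What to change.** 1. Reconcile the 3-month waiting and follow-up statements with the 2-month break, and state that the T4 assessment is taken before any WL participant starts a course. How long each period should be is for the investigators to settle.
2. List WEMWBS, PHQ-9 and GAD-7 at T4 in both arms beside UCLA. Specify the AG-WL difference at T4 as the controlled estimate about 2 months after the course, adjusted for the T1 score where the scale was given at T1 (UCLA is not listed there).
3. Report AG at T5 as uncontrolled follow-up at about 5 months. Draw no AG-versus-WL treatment conclusion from T5 or from a group-by-time term over T4 to T5.
4. Bring the simulation's time points into line with the visits at which the primary outcomes are collected.

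**Cost.** 14 + 9 + 7 = 30 self-report items at a visit both arms already attend, one added contrast and corrected labels. The downside is slightly more participant burden at T4.

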# here come the parameters that I will pass to this function
# from https://hqlo.biomedcentral.com/articles/10.1186/1477-7525-10-156
mean T1 <- 43.5 # the biggest trial in that list, the PEIP
sd T1 <- 10.4 # from that trial
d <- -0.5 # stipulated effect size of difference

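### Model (1) has neither a person term nor a course term, so the SE of b3 is not valid; once repeated measures are handled, ignoring the arts courses in AG makes the test anti-conservative

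*Protocol*

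**What the plan says.** Under Design, culture institutions such as an opera house, a museum and a theatre "presented their action plans for interventional courses", and "Potential participants declared their preference for the interventional course such as dance, cinema etc". Participants are then randomised to AG or WL, with stratification at each site. WL waits 3 months before receiving the intervention.

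Under Model, the analysis is written out as "y ~ b0 + b1xtreatment_group + b2xtime + b3xtreatment_groupxtime + covariates (1". The plan continues: "The inference of interest for the model concerns b3, the interaction term". The test statistic is b3 divided by its SE, defined only by "Where SE is the standard error for coefficient b3", and the threshold is fixed: "And 1.96 is the critical value for statistical significance at alpha = 0.05". The covariates are still open: "covariates denote covariates at randomisation (DETERMINE".

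The code under Target Sample Size per Arm fits aov with time, group and their interaction, and no Error term. It simulates four time points with "d <- -0.5 # stipulated effect size of difference" and SD 10.4. The correlation is 0.6 in the parameter list and 0.5 in the live code. It scans 20 to 300 per arm; no chosen N is printed. No number of courses, course size or ICC appears anywhere.

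**The concern.** People on one course share a teacher, an institution, content and probably classmates, so their changes over the 12 weeks may be alike. In the randomised comparison this can arise in AG only, a partially nested design. Each person also contributes several rows, and these are correlated. A valid SE for b3 has to reflect both features; the stated one reflects neither.

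This is more than a detail left for a later analysis plan, because the protocol itself fixes the model, the statistic and the critical value. An open covariate list does not repair it: a covariate main effect removes neither within-person correlation nor between-course variation in slopes. At stake are the true error rate of the primary test and the validity of a sample size derived from the same model.

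**Working it through.** **Inputs from the protocol.** Alpha 0.05 with critical value 1.96 (taken as two-sided), power 0.8, d = 0.5 (a code comment says 0.4), r = 0.6 or 0.5, four simulated time points.

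**Assumed, not in the protocol.** People per course m = 8 to 20; ICC of change within a course = 0.02 to 0.10; equal arms.

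**The plan's own figure.** No N is printed to reproduce. Rerunning the plan's simulation at d = 0.5 gives power 0.747 at 140 per arm and 0.856 at 160 (r = 0.5), or 0.742 and 0.857 (r = 0.6). It therefore implies roughly 140 to 160 per arm, or about 240 if d = 0.4.

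**Step 1: no course effect, SE as written.** With equal correlation r between time points, the true variance of a difference in slopes is (1 − r) times the variance that row-independent least squares assigns to it. True alpha is 2[1 − Φ(1.96/√(1 − r))].
- r = 0.5: 1.96/0.707 = 2.77, alpha 0.006.
- r = 0.6: 1.96/0.632 = 3.10, alpha 0.002.

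**Step 2: person-level SE, courses ignored.** Design effect in AG: DE = 1 + (m − 1)ICC. Variance inflation of b3: VIF = (1 + DE)/2. Size: 2[1 − Φ(1.96/√VIF)].

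| m | ICC | DE | VIF | two-sided size |
|---|---|---|---|---|
| 8 | 0.02 | 1.14 | 1.07 | 5.8% |
| 12 | 0.05 | 1.55 | 1.275 | 8.3% |
| 12 | 0.10 | 2.10 | 1.55 | 11.5% |
| 20 | 0.10 | 2.90 | 1.95 | 16.0% |

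Simulation at 120 per arm with m = 12 agrees: about 8% at ICC 0.05 and 12% to 13% at ICC 0.10.

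**Step 3: both faults together, SE as written.** The ratio of true to model variance is (1 − r)(1 + DE)/2.
- m = 12, ICC 0.05: 0.5 × 2.55/2 = 0.64, alpha 0.014 (r = 0.5); 0.4 × 2.55/2 = 0.51, alpha 0.006 (r = 0.6).
- m = 20, ICC 0.10: 0.5 × 3.90/2 = 0.975, alpha 0.047 (r = 0.5; simulation gave 0.057); 0.4 × 3.90/2 = 0.78, alpha 0.026 (r = 0.6).

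The ratio reaches 1 when (m − 1)ICC = 2 (r = 0.5) or 3 (r = 0.6). That is ICC 0.18 or 0.27 at m = 12, and 0.11 or 0.16 at m = 20.

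**The case against.** The strongest objection is that the test as written is not anti-conservative. A reader might infer that any course effect pushes its false-positive rate above 5%. The plan does not support that: its SE treats rows, not people, as independent, and Step 3 puts alpha well below 5% over most of the assumed range and at about 5% only in the extreme corner. This objection stands. It does not make the SE valid: two opposite errors whose net result depends on r, m and ICC do not give a controlled 5% test, and repairing only the first exposes the second.

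A reader might also infer that power falls from 80% to between 77% and 52%. Those figures assume a person-level test sized to exactly 80%. The plan's simulation instead implies about 140 per arm or more. There, a person-level comparison of change at r = 0.5 has z = 0.5/(√(2 × 0.5) × √(2/140)) = 4.18 and power Φ(4.18 − 1.96) = 98.7%. At VIF 1.95 it is Φ(4.18/1.396 − 1.96) = 85%. This is a normal approximation that ignores the loss of degrees of freedom when courses are few, but it shows that a fall below 80% is not established.

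Three further limits stand. A course difference that is constant over time cancels from b3, and an effect common to all courses is the treatment effect; only between-course variation in change matters. The protocol defines no confidence interval, so an interval is affected only if one is reported from the same SE. That several AG participants share a course is a fair inference from delivery by courses, not an explicit statement.

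One could also treat the listed courses as the fixed and only target of inference. That is a legitimate choice, but the protocol does not make it, and model (1) has no course term of either kind.

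**Conclusion.** The point holds in a limited form. The SE of b3 is not valid, because it ignores both the repeated measures and the course structure of AG. As written, the test is conservative without a course effect (alpha about 0.002 to 0.006), and it stays below or near 5% for m up to 20 and ICC up to 0.10. With a person-level SE that still ignores courses, size would be 5.8% to 16%.

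The structural fault is clear from the protocol; its size is not, because m and ICC are assumed. The figures also rest on equal correlation between time points, equal arms, and course clustering of change in AG only. No shortfall below the planned power of 0.8 is claimed.

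**What to change.** - Record the course that each AG participant actually attends. Declared preference is not stated to equal attendance.
- Replace model (1) with a repeated-measures mixed model: a person-level random effect or covariance, plus a random course effect on change in AG only, with Satterthwaite or Kenward-Roger degrees of freedom.
- Declared course preference may be added as a pre-randomisation covariate in both arms. It does not replace the course random effect.
- Rerun the power simulation with this model and quote power over a stated range of ICC and course size.

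The cost is one recorded variable, revised analysis wording and a rerun of the simulation. If there are few courses, degrees of freedom fall, and any interval will be wider than one from a person-level analysis that ignores courses.
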